During our pilot study 100% of the patients completed the 2 month follow-up assessment;¹¹ however we are realistic and recognize that such retention rate is very optimistic for this study. Thus, in this study we estimate the attrition to be 10% at the 3 months follow-up. We also estimate the attrition to be 15% at 6 months, based on our pilot work and other studies with similar populations and timeframes. We will compare baseline characteristics between patients with and without the assessment at 3 and 6 months to assess potential biases in the complete case analysis. We will also try to obtain reasons for study drop out to assess the missing data mechanism (missing completely at random, missing at random, non-ignorable missingness). We will use several missing data methods for imputing data and re-analyze using intention to treat (as randomized) to assess the impact of missing data on our conclusions as recommended.⁹⁷ We

PRINCIPAL INVESTIGATOR (LAST, FIRST, MIDDLE): [name]

will first use multiple imputation (with M=10 imputations) which assumes the data are missing at random. Since the data could be missing not at random, we will use another approach of assigning the lowest observed scores for missing values differentially by treatment group (non-ignorable missingness). The approach assumes the missingness is directly related to the value of the missing data, i.e., the people who are missing data on function have worse function scores (did not come in for assessment because function was worse). Results of all approaches to missing data will be presented in the primary paper for our study. If our significance and interpretation of our treatment effect vary depending on the method of imputation, we will view any conclusions cautiously.

PATIENT POPULATION

Detailed reasoning of inclusion criteria is provided in Human Subjects.

Subjects will be included in the study if they underwent a unilateral TKR 2 to 4 months prior to study, are older than 60 years of age, experience functional limitation in daily activities (score in the WOMAC-PF of at least 9 points), *speak English sufficient to understand study instructions*, are willing to be randomized to one of the 3 treatment groups, and have medical clearance to participate in the study.

Subjects will be excluded if they:

- Have absolute or relative contraindications to exercise testing as established by the American College of Cardiology/American Heart Association;^{99,100}
- Have a history of uncontrolled cardiovascular disease or hypertension;
- Are unable to walk 50 meters without an assistive device and to comfortably bear weight on the surgical knee;
- Have a history of muscular disease (e.g., muscular dystrophy) or neurological disorder that may affect lower extremity function (e.g., CVA, neuropathy, Parkinson's disease, multiple sclerosis);
- Regularly participate in structured exercise;
- Have a terminal illness;
- Are planning to have another joint replacement during the next 12 months;
- Do not plan to be around during the next 12 months (e.g., plan to travel, relocate to another city, etc.).

Inclusiveness of Different Populations- The make-up of the patient population of this study will be representative of the general population of older adults who undergo TKR in the US with respect to age, race, socioeconomic status, and general health. We will be sure to specifically target patients who provide important perspectives, such as patients who are ethnically diverse and have multiple chronic conditions or impaired access to healthcare because of age or disabilities. We will include subjects 60 or older because most patients undergo TKR after 60 years of age. While a higher number of patients are undergoing TKR at a younger age, they are still the minority and would be in better health than the older group. We did not impose an upper age limit for eligibility because many patients over 90 years undergo TKR. We believe that as long as they are cleared to do the surgery and they believe the TKR will be helpful to them, they should be in the study. Last, older patients who undergo TKR also have multiple comorbidities such as obesity, diabetes, high BP and arthritis of other joints^{19,20,101} and they will be included. Enrolling older adults with coexisting comorbidities will improve generalizability and clinical relevance of study results. With respect to race and socioeconomic status, we have been very successful recruiting an adequate proportion of African American and lower income research subjects and, as in the proposed study we will use similar recruitment strategies we expect similar success.

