- **Knee Impairments** – We hypothesize that patients with increased knee pain, decreased knee range of motion, and lower extremity muscle strength who participated in the outpatient rehabilitation will be able to improve physical function whereas the ones who participated in the community-based group exercise classes will not. Knee pain in the surgical and non-surgical knee will also be measured using an 11-point pain scale. Knee range of motion will be measured by a standard goniometer. We will measure the strength of the muscle groups that have been related to the outcome of TKR^{45,79} including knee extension strength and hip abduction strength measured using an isokinetic dynamometer (Biodex System 4 Pro, Shirley, NY) as we described before.⁴⁵

Capturing Potential Harm of Interventions- Growing evidence suggests that regular physical activity does not have deleterious effects on the survival of the prosthesis.^{80,81} The exercises we propose are not expected to cause any harm because they exert relatively low forces over the prosthesis.⁸²⁻⁸⁵ Regardless of the anticipated safety of the exercises, we will ascertain that interventions offer no harm by closely monitoring adverse events:

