- **Adverse Events-** We will capture information on (1) changes in knee pain, swelling, and stiffness; (2) difficulty to bear weight on the surgical leg; (3) falls; (4) if subject has been hospitalized or disabled (> ½ day in bed or required to cut back on routine activities), and; (5) if subject had a TKR on the other knee. For information on falls we will ask subjects if they have had any falls using a 2-3 minute questionnaire developed at the Pittsburgh Pepper Center. One-week test-retest reliability (Kappa) was established as 0.89 in a sub-sample of 43 participants enrolled in a Pepper Center observational cohort study of older adults ([name] unpublished data). Falls will be defined as unintentionally coming to rest at a lower position. In this study serious adverse events (SAEs) are defined as hospitalization, death, or permanent disability. Adverse Events (AEs) are defined as exercise-related discomforts that remains for 3 days or longer (e.g., muscle and joint soreness/pain), minor injuries (e.g., strains, sprains), and non-injurious falls. Transient side effects are defined as complaints of increased pain, stiffness, or muscle weakness for periods of 2 days or shorter. We will compare the measures of harm such as adverse events and attrition by treatment interventions. If they differ between groups, they will be used as a covariate in the final outcome analysis.

We will also monitor attrition, adherence and co-interventions:

- **Attrition** is defined in this study as the number of patients dropping out of the study in each group.
- **Adherence** to intervention will be estimated by the proportion of sessions attended in each group and the proportion of patients missing each session. Adherence to the individualized outpatient exercise will be recorded by the physical therapist. Adherence to the group exercise classes will be obtained from reports generated by the community centers.
- **Co-interventions** will be queried during every assessment. Some subjects could decide to seek additional treatment options while enrolled in the study. We will ask about additional treatment sought (e.g., seeking specialized care), and participation in exercises besides the ones prescribed by the study. If the subject participated in additional exercises, we will record the frequency, duration, and type of the exercise and will analyze these data for their potential effect on the primary outcome.

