Calculations of sample size were based on the primary endpoint of WOMAC-PF at 3 months. We propose to recruit a total of 240 subjects (96 in each exercise arm and 48 in the usual care group) to allow approximately 86 subjects in each exercise arm and 43 in the usual care group available for a complete case analysis at 3 months (assuming 10% attrition at 3 months). We propose a larger number of subjects in both exercises groups (outpatient rehabilitative exercise and community-based group exercise) because we expect a moderate effect size between these two interventions; whereas we propose a smaller number of subjects in the usual care group because we expect a large effect size between the usual medical care group and either of the exercise groups. Thus, with an alpha level of 0.05, 2 tails test, a sample size of 172 (n=86 in each exercise group) will provide 81% power to detect a difference as small as 3.3-point difference between the two exercise groups in WOMAC-PF (SD of 7.7 from our pilot work).¹¹ This would correspond to a difference in less than 2 activities (out of the 17 queried in the WOMAC-PF) having improved from “about moderate difficulty” to “no difficulty”. The sample size of 43 in the usual medical care group will provide 80% power to detect a difference of 5.2-point difference in WOMAC-PF between the usual medical care group and any exercise group. Power analysis was conducted in NCSS/PASS. Moreover, this sample size will provide adequate power (above 80%) to test the hypothesis related to the secondary outcomes (performance-based physical function and physical activity). For example, we will be able to detect differences between the two exercise groups as small as 0.7 sec in the stair climbing test, 0.4 in the chair-rise test, 0.02 m/sec in walking speed, 1.4 sec in the single leg stance, and 35 min/day in light intensity physical activity (based on SD of our own preliminary data). The differences we will be able to detect between the usual care and any intervention groups are as small as 1.01 sec in the stair climbing test, 0.54 in the chair-rise test, 0.03 m/sec in walking speed, 1.6 sec in the

PRINCIPAL INVESTIGATOR (LAST, FIRST, MIDDLE): [name]

single leg stance, and 49 min/day in light intensity physical activity. These differences are smaller than the known minimal detectable changes for these outcomes.⁸⁸⁻⁹⁰

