We will calculate dropout rates as proportions of subjects randomized and as a cumulative probability of remaining in the study using survival analysis techniques such as the product-limit estimator. This statistic can be estimated at various times following randomization and take into account when dropouts occur. Descriptive statistics will be used for reporting and evaluating implementation of the exercise protocols including the proportion in attendance for each session and the average number of sessions attended by group. The two intervention groups require the same number of exercise sessions (2 per week) for 3 months. To assess the impact of non-adherence, we could conduct a per-protocol analysis for the treatment effect but this would likely result in a biased estimate of the treatment effect due to selection bias of those who are more likely to adhere not representing a true random sample of trial participants. We propose to explore using instrumental variable methodology to estimate the efficacy for our interventions in the presence of non-adherence.⁹⁴ Instrumental variables have been mainly used in the econometrics⁹⁵ but have been proposed as a useful tool in estimating dose-response effects in psychological treatments where participants are expected to attend multiple sessions as part of the intervention protocol.⁹⁶ We propose to use the two-stage IV methods which can be easily implemented in Stata software using simple linear structural models for the effect of sessions attended on the primary outcome of function. We will also calculate the 6-month incidence (and 95% CI) of individual adverse events by organ system and relatedness to the study for each group. We will estimate the incidence of adverse events with specific focus on those deemed definitely, probably, or possibly related to interventions. For adverse events, clinical judgments will be considered more important than statistical testing.

Dropout and missing data analyses

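### The plan promises to establish that the exercise programmes do no harm, but it plans no interval for the excess harm over usual care, and 48 usual-care patients cannot support that conclusion

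*Combined protocol and SAP*

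**What the plan says.** All references are to the Combined protocol and SAP.

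- **Capturing Potential Harm of Interventions** states the aim for safety: "we will ascertain that interventions offer no harm by closely monitoring adverse events". The Design Overview names harms alongside effectiveness in the question that the trial is to answer.
- **Adverse Events**, in the same section, says "We will compare the measures of harm such as adverse events and attrition by treatment interventions". What follows from a difference is this: "If they differ between groups, they will be used as a covariate in the final outcome analysis". No test, error rate, margin or tolerable excess is given.
- **Exploratory Hypothesis**, under Data Analysis, expects fewer adverse events, mainly falls, in the two exercise groups than under usual care. It plans a 6-month incidence with a 95% interval for each group, by organ system and relatedness, and adds: "For adverse events, clinical judgments will be considered more important than statistical testing".
- **Sample Size** sets "240 subjects (96 in each exercise arm and 48 in the usual care group". The small usual-care arm is justified there and under Randomization by the large effect expected on function, not by any harm.

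**The concern.** A claim of no harm relative to usual care is a claim about a difference. An incidence with its own interval in each arm describes that arm. It does not say how much of the harm is due to the programme, or how large an excess the data leave open. The one comparison between arms that is planned leads to an adjustment of the efficacy model, not to a safety conclusion.

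The size of the usual-care arm makes this matter. It was chosen for a large expected difference in WOMAC-PF, and that reasoning does not carry over to harms. If an uncommon harm were doubled by exercise, the observed rates could easily look similar. A report written to the stated aim could then reassure patients and physicians more than the data allow.

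**Working it through.** **The plan's own figure.** The only power statements concern efficacy outcomes. The main one is "81% power to detect a difference as small as 3.3-point difference between the two exercise groups in WOMAC-PF (SD of 7.7 from our pilot work", with 86 per arm. By normal approximation, 3.3 / (7.7 × √(2/86)) = 3.3 / 1.174 = 2.81; 2.81 − 1.96 = 0.85; Φ(0.85) = 80%. This agrees with the stated 81% to within about a point. There is no harm figure to reproduce.

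**Inputs for harm.**
- Arm sizes at full enrolment: 96, 96 and 48 (Sample Size), so 96 v 48 for one exercise arm and 192 v 48 pooled.
- Test level: the plan specifies none for harm. I borrow "with an alpha level of 0.05, 2 tails test" from the efficacy calculation.
- Usual-care event rates: not in the documents. I assume 5%, 10%, 20% and 30%.

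**Step 1: chance of missing a true doubling.** Reject if |pE − pU| / √(p̄(1 − p̄)(1/nE + 1/nU)) ≥ 1.96, where pE and pU are the observed proportions and p̄ is the pooled proportion. Power is the sum of the two binomial probabilities over all tables that reject. The miss rate is 1 − power.

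| Usual care → exercise | Missed, 192 v 48 | Missed, 96 v 48 |
|---|---|---|
| 5% → 10% | 85.9% | 86.5% |
| 10% → 20% | 64.4% | 67.9% |
| 20% → 40% | 22.9% | 30.5% |
| 30% → 60% | 3.2% | 6.3% |

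With the 15% attrition assumed at 6 months (96 × 0.85 = 81.6; 48 × 0.85 = 40.8; so 82 v 41), the first two rows for one arm rise to 89% and 73%.

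**Step 2: the excess left open when observed rates are equal.** This step depends on neither a test nor a doubling. The Newcombe upper limit for pE − pU at equal observed rate p is √((uE − p)² + (p − lU)²), where uE is the upper Wilson 95% limit in the exercise group and lU the lower Wilson limit in usual care.

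At 10%: lU = 4.28% (n = 48); uE = 15.06% (n = 192) or 17.62% (n = 96).
- Pooled: √(5.06² + 5.72²) = 7.6 points.
- One arm: √(7.62² + 5.72²) = 9.5 points.

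| Equal observed rate | Upper limit, 192 v 48 | Upper limit, 96 v 48 |
|---|---|---|
| 5% | +5.3 points | +7.2 points |
| 10% | +7.6 | +9.5 |
| 20% | +10.9 | +12.7 |
| 30% | +13.0 | +14.8 |

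For commoner events a doubling becomes easier to detect, but the absolute excess left open grows.

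**Step 3: no events in an arm.** The exact upper limit of a two-sided 95% interval is 1 − 0.025^(1/n). For 0/96 it is 3.8%; for 0/48 it is 7.4%.

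**The case against.** The strongest reply is that the sentence on no harm introduces a list of what will be recorded. On that reading it describes surveillance and is not an analysis criterion. The harm analysis itself is under the Exploratory Hypothesis, where relatedness is assessed and clinical judgement outranks testing. Harm is an exploratory aim, and a trial of 240 patients will always have little power for uncommon events. A reader can also derive risk differences from the incidences in each arm.

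Much of this stands, and it rules out a stronger reading. A reader might infer that failing to find a significant difference is the plan's only route to a finding of no harm. The documents do not say so: no passage attaches a safety conclusion to a test, and the stated preference for clinical judgement points the other way.

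It does not remove the gap. If the sentence is loose, correcting it is easy, and the interval for the difference is still missing. Clinical judgement about excess harm needs the excess and its upper limit in front of it.

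A second objection limits the remedy. The definition of an adverse event is partly tied to exercise, since it includes discomfort arising from exercise that lasts three days or more. Patients under usual care cannot readily have that component, so comparing the composite would tilt towards excess harm by definition.

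**Conclusion.** The point holds as a mismatch between the stated safety aim and the planned analysis. No interval for the excess over usual care is planned. At every rate checked, equal observed rates would leave open an excess of about 5 to 13 points pooled, or 7 to 15 points for one exercise arm. That does not amount to no harm. Whether such an excess is tolerable is a clinical judgement, which the documents do not make.

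A reader might also infer that a doubling of harm would usually be missed in this design. That is true only for harms at about 10% or below in usual care. The miss rate falls to about 23% (pooled) or 30% (one arm) at a 20% rate, and to 3% or 6% at 30%. The documents do not say where falls, hospitalisations or knee symptoms lie on this scale.

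The figures rest on assumed rates, full enrolment, harms counted as patients with at least one event, and a test level borrowed from the efficacy calculation. The plan should be changed, but the trial design need not be.

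**What to change.** 1. Under Capturing Potential Harm of Interventions, replace the promise to ascertain no harm with a commitment to estimate the excess harm of each exercise programme over usual care and to report the largest excess that the data do not rule out.
2. Under the Exploratory Hypothesis, add the risk difference against usual care with a Newcombe 95% interval, for each exercise arm and for both pooled. Restrict it to harms defined alike in all arms: serious adverse events, and the proportion of patients with any fall. If falls are analysed as a number, as the hypothesis suggests, give a rate ratio or rate difference with its 95% interval.
3. Keep adverse events defined through exercise descriptive by arm, or compare only components recorded in the same way in every arm, such as knee symptoms.
4. State that the absence of a significant difference will not be reported as no harm. Where an arm has no serious adverse events, report the exact upper limit (3.8% for 0/96).

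The cost is a few sentences and a few intervals from data already being collected, with no added patients or visits. The downside is a more guarded safety statement.

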Hypothesis 2- A group of baseline biomedical and psychosocial measures will associate with treatment response.

Each subject will be classified as a responder or non-responder based on a minimum change score of 20% in BOTH the WOMAC-PF and the composite score of functional performance at 3 months, thus yielding a binary outcome. Baseline variables will be summarized separately for responders and non-responders. Unadjusted odds ratios will be estimated using univariate logistic regression. To consolidate potential predictors, we will test for collinearity among baseline variables that are associated with response. Baseline measures associated with response at the $p<0.15$ level in unadjusted models will be added to multivariable logistic regression models to assess predictors of treatment response. We will limit the number of predictors going into any one model to no more than one predictor per 10 responses (or 10 non-responses, whichever is less); if more variables are significant, the model will be limited to the most significant variables, after adjusting for those deemed a-priori to be clinically significant. We expect different predictors for each group. For example, patients with worse physical function and impairments (e.g., limited range of motion and muscle weakness) will do better with individual outpatient exercise whereas those with heightened psychosocial factors (e.g., anxiety and depressive symptoms) will respond better to group exercise in the community.^{48,70-72}

Exploratory Hypothesis- Adherence and co-interventions will be similar in all groups. The attrition rate and adverse events- mainly number of falls- will be lower in Groups 1 and 2 compared to Group 3.

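### The discomfort part of the adverse event definition is tied to exercise, so it counts differently by arm, and falls with a more-than-minor injury but no serious outcome have no adverse event category

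*Combined protocol and SAP*

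**What the plan says.** The Adverse Events item under Capturing Potential Harm of Interventions sets three classes of event:

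- Serious: "serious adverse events (SAEs) are defined as hospitalization, death, or permanent disability".
- Adverse events: "Adverse Events (AEs) are defined as exercise-related discomforts that remains for 3 days or longer", followed by "minor injuries (e.g., strains, sprains), and non-injurious falls".
- Transient: "Transient side effects are defined as complaints of increased pain, stiffness, or muscle weakness for periods of 2 days or shorter".

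The same item collects data more widely than these classes. On falls it says "For information on falls we will ask subjects if they have had any falls using a 2-3 minute questionnaire", and "Falls will be defined as unintentionally coming to rest at a lower position", with no condition on injury or arm. It also asks "if subject has been hospitalized or disabled (> ½ day in bed or required to cut back on routine activities").

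The item goes on to say that harms such as adverse events and attrition will be compared by treatment arm, and that they will enter the final outcome analysis as covariates if they differ. The Exploratory Hypothesis under Data Analysis predicts: "The attrition rate and adverse events- mainly number of falls- will be lower in Groups 1 and 2 compared to Group 3". The text after it plans 6-month incidence with a 95% confidence interval for each group, by organ system and by relatedness to the study.

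**The concern.** Comparative harm is one of the three focuses named in the Design Overview. A fair comparison needs the same event to be counted in the same way in each arm. Here the discomfort item asks about cause before the event is counted, and the cause it asks for is the treatment given in two of the three arms. Patients in structured exercise at enrolment are excluded, so a usual-care patient will typically have no exercise to which soreness could be attributed.

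Three things are at stake. The adverse event rate could look worse with exercise when the true rates are equal, which also works against the stated hypothesis. A difference produced by the definition could trigger adjustment of the outcome model for a variable measured after randomization. And on the falls side, a harmless fall is an adverse event while some more harmful falls carry no label at all.

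**Working it through.** The plan gives no adverse event rate, so there is no figure to reproduce. The check sets the definitions side by side, then illustrates the size under stated assumptions.

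**1. Discomfort lasting 3 days or longer**

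| Patient | Counted as an adverse event? |
|---|---|
| Exercise arm, attributed to the exercise | Yes |
| Usual care, has taken up exercise, attributed to it | Yes |
| Usual care, not exercising | No |

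The transient class (2 days or shorter) has no such condition, so shorter soreness is treated alike in all arms and longer soreness is not. The analysis text reports incidence by relatedness, which presupposes that unrelated events are recorded. For discomfort, the definition has already removed them.

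**2. Falls**

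| Fall | Class under the text |
|---|---|
| No injury | Adverse event |
| Strain or sprain | Adverse event, as a minor injury |
| Hospitalization, death or permanent disability | Serious adverse event |
| More-than-minor injury with none of these (for example, a fracture treated as an outpatient) | None |

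The last row is still a fall under the plan's own fall definition and is asked about by questionnaire.

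**3. Illustration of the discomfort bias**

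Input from Sample Size: 96 + 96 = 192 exercise and 48 usual-care patients. The rest are assumptions that the documents do not supply:

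- q: true risk of discomfort lasting 3 days or longer, equal in all arms.
- b = 0.15: risk of a fall or minor injury that counts as an adverse event, equal in all arms and independent of discomfort.
- s: share of usual-care discomfort that is classed as exercise-related. All discomfort in the exercise arms is so classed.

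Labelled rate with exercise: pE = 1 − (1 − q)(1 − b). 
Labelled rate with usual care: pU = 1 − (1 − qs)(1 − b). 
Spurious difference: pE − pU = q(1 − s)(1 − b).

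For q = 0.20 and s = 0: pE = 1 − 0.80 × 0.85 = 0.320, pU = 0.150, difference = 0.170.

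The plan does not say how a difference would be judged, so a two-sided 5% test is assumed. The chance that it declares a difference is Φ[(pE − pU − 1.96·SE0)/SE1]. SE0 uses the pooled proportion and SE1 the separate proportions. For the same case:

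- Pooled proportion = 0.8 × 0.320 + 0.2 × 0.150 = 0.286.
- SE0 = √[0.286 × 0.714 × (1/192 + 1/48)] = 0.0729.
- SE1 = √[0.320 × 0.680/192 + 0.150 × 0.850/48] = 0.0616.
- Φ[(0.170 − 1.96 × 0.0729)/0.0616] = Φ(0.44) = 0.67.

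| q | s | Exercise | Usual care | Spurious difference (points) | Chance of declaring a difference |
|---|---|---|---|---|---|
| 10% | 0 | 23.5% | 15.0% | 8.5 | 22% |
| 20% | 0 | 32.0% | 15.0% | 17.0 | 67% |
| 30% | 0 | 40.5% | 15.0% | 25.5 | 95% |
| 10% | 0.25 | 23.5% | 17.1% | 6.4 | 14% |
| 20% | 0.25 | 32.0% | 19.3% | 12.7 | 40% |
| 30% | 0.25 | 40.5% | 21.4% | 19.1 | 71% |
| 10% | 0.5 | 23.5% | 19.3% | 4.2 | 8% |
| 20% | 0.5 | 32.0% | 23.5% | 8.5 | 19% |
| 30% | 0.5 | 40.5% | 27.8% | 12.7 | 36% |

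For one exercise arm against usual care (96 v 48), the s = 0 chances are 21%, 60% and 90%.

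**4. Illustration of the falls gap**

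Assume a proportion F of the 240 patients fall and a share k of those falls are of the unlabelled kind. With F = 10% and k = 5%, 240 × 0.10 × 0.05 = 1.2 fallers lack a label. With F = 30% and k = 20%, it is 240 × 0.30 × 0.20 = 14.4. These are missing labels, not missing data.

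**The case against.** The strongest reply is that the gap lies in labels on only part of the definition, and that the plan half repairs it elsewhere. Much of this stands.

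A reader might infer that usual care cannot score adverse events on equal terms at all. The text does not support that. By its grammar, the exercise condition attaches to discomforts only. Minor injuries and non-injurious falls can be scored in any arm. The Usual medical care section also allows patients in that arm to take up exercise, and records it, so even the discomfort item is not closed to them.

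A reader might also infer that every injurious fall without hospitalization is lost, or that the falls count is short by some fraction. That does not follow either. A fall with a strain or sprain is a minor injury, and one causing permanent disability is serious without admission. All falls are asked about whatever the injury. The hypothesis speaks of the number of falls, and nothing says this number must be built from the adverse event label. An outpatient-treated fracture would probably also appear under the question on disability and reduced activities.

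The planned grading of relatedness suggests that the authors meant to record unrelated events too. That favours reading the matter as an inconsistency between two sections, but it does not remove it: anyone following the written definition would leave out unrelated discomfort before relatedness could be graded.

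Finally, the hypothesis is exploratory and the plan ranks clinical judgement above testing for adverse events. That limits the consequences. The between-arm comparison and the covariate rule are nevertheless both stated.

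**Conclusion.** The point holds in two limited parts.

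First, the discomfort component depends on attribution to exercise. Followed as written, it biases the between-arm adverse event comparison, and the covariate rule that depends on it, against the exercise arms, and it conflicts with reporting by relatedness. The size cannot be derived from the documents. Under the assumptions shown, the spurious difference runs from about 4 to 25.5 percentage points and shrinks to nothing as s approaches 1.

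Second, a fall with a more-than-minor injury but no hospitalization, death or permanent disability is in neither the adverse event nor the serious adverse event count, although the questionnaire captures it as a fall.

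The change is worth making because harm is a stated focus and the remedy is small. Nothing here shows that the fall data themselves are incomplete.

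**What to change.** - For the adverse event count compared between arms, remove the exercise condition, so that discomfort lasting 3 days or longer counts in every arm whatever its cause. Judge relatedness separately afterwards, as the analysis text already plans.
- In the harm comparison, count every fall reported on the falls questionnaire, injurious or not, and show injurious falls as a subset where injury is recorded.

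The cost is a change of definition and higher total adverse event counts. Table 1 already schedules adverse event collection in months 1.5, 3, 4.5 and 6, so no new contact is needed. The documents do not show whether the falls questionnaire records the number of falls or injury status. This should be checked, and if it does not, an item would have to be added to report them. A model for fall counts, such as a negative binomial rate ratio, is optional: it would suit a hypothesis about the number of falls, but it needs those counts and the hypothesis is exploratory.
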